Furthermore, we will also analyze the iron status, as previous studies have shown an interaction between iron status and omega-3 fatty acids. For the correct interpretation of the iron status, we will ask all patients to provide us with information about iron and other vitamin supplementation they might have taken before study start. Patients who have already been enrolled in the trial will be recontacted and asked to provide the missing information.

The aim is to collect all blood samples for all subjects. However if subjects do not want to have subsequent blood samples drawn or urine and saliva collected, they can still participate in the study. In a separate consent form, subjects will be asked to provide blood for BioBanking in accordance with the Swiss legal regulations. Over the course of the entire study, a total amount of approximately 50 ml blood will be maximally drawn: After signing the consent from 3x3ml to perform standard clinical laboratory tests, 4 ml for bioactive lipids, 10 ml for (epi)genetic markers, 10 ml for immune markers, 10ml for specialized pro-resolving lipid mediators (SPM), and 3ml for mitochondrial metabolism will be drawn. The laboratory blood sampling must be done for all subjects after written informed consent has been obtained as this information is required for the minimization procedure (stratification). The further bloods shall be taken if possible, but are not mandatory for participation in the clinical trial. If too many subjects refuse the additional blood samples, total sample size may need to be reconsidered to be able to address secondary and tertiary outcome measures.

In addition, patients will provide a urine sample for later drug screening and F2 isoprostane, and a saliva sample to measure cortisol concentrations.

In addition, cortisol and other hormones will also be measured with a string of hair, which will be sampled at 6 weeks and at study end on condition of the patient's consent, to allow a continuous steroid profile over the whole study period. In addition, a short hair protocol will be filled in. If patients provide consent for storage of material in the BioBank, the remaining hair will be stored in the BioBank for potential future analysis.

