11.4.3 Secondary Analyses

Important CDRS-R-related outcome measures include response and remission. Remission is defined as a CDRS total score <28 and response is defined as a 30% drop in CRDS total baseline score (post placebo lead in). Participants using additional antidepressants, days on trial before the additional antidepressant, KIDscreen-CAT-27, and DIKJ will also be analyzed. Supportive endpoints include the number of days in the hospital and the amount of outpatient service use. For analysis details related to secondary and supportive outcomes of the primary trial reporting, please see the separate Statistical Analysis Plan document.

For further secondary outcomes, we will apply the same statistical strategy as for the primary outcome measures. Analysis will include changes in overall and subscores of the in chapter 9.2 listed secondary outcome instruments. We will analyze CDRS-R subscores, DIKJ, BHS, BAI, SIQ-Jr, IES-27, KIDscreen-CAT-27, PSS-10, and Resilience Scale scores and compare them between the treatment groups.

Furthermore, we'll run the following analyses to test our secondary working hypotheses:

- **WH3a:** We will test the effect of inflammatory mediators on the efficacy of omega-3 treatment by introducing an additional continuous factor (ratio between pro- and anti-inflammatory markers) into the linear regression model described in 11.4.2.
- **WH3b:** We will calculate an omega-3 index based on red blood cell Omega-3 fatty acids content and introduce an additional binary factor (n-6/n-3 Omega ratio < 3 vs. n-6/n-3 Omega ratio > 5) into the linear regression model described in 11.4.2.
- **WH3c:** We will test whether direct metabolites of EPA are a strong predictor of Omega-3 fatty acids by introducing additional continuous factors (levels of HETEs and E-series-resolvins at baseline) into the linear regression model described in 11.4.2

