6.2 Difference in Proportion of Responders

A two-proportion z-test would require 97 participants per treatment arm to have 80% power to detect a difference in response of 20% (with 60% response in the treatment group and 40% response in the control group) at the 0.05 two-sided significance level. Accounting for a 10% loss to follow-up results in a total sample size of 216 participants.

7 Statistical analyses

Analysis sets The following analysis sets are defined in accordance with the ICH-E9 guidelines:

- The full analysis set (FAS) includes all randomized subjects. The FAS will be used for 'as randomized' evaluation. Only in exceptional cases may subjects be excluded from the FAS. In such cases the reason for exclusion will be justified and documented.
- The safety analysis set includes all randomized subjects receiving at least one dose of randomized treatment. The safety analysis set will be used for 'as treated' evaluation.

Baseline comparability of randomized groups Baseline descriptive variables of participants (including antidepressant use) will be summarized overall and by treatment arm using suitable measures of central tendencies and variability for continuous data (means or medians, SD or IQR) and frequencies and proportions for categorical data. No hypotheses are tested.

The number of participants lost to follow-up, initiating antidepressants, and adhering to the protocol will each be tabulated by treatment arm and visit. Baseline characteristics will also be summarized across the groups of participants completing the trial, lost to follow-up, and initiating antidepressant use.

General statistical considerations Statistical analysis results will generally be presented as point estimates with two-sided 95% confidence intervals. A limited number of analysis results will additionally be reported with p -values, which will be interpreted as indicative of superiority when the value is less than 5% and the estimated treatment contrast favors the omega-3 treatment arm.

Descriptive statistics for all efficacy and safety endpoints will be presented according to treatment arm.

The baseline values are collected at visit 1 (0 weeks), which is the first week after the lead-in phase. Further measurements are taken at visits 2 through 5 at 6, 12, 24, and 36 weeks.

The clinical trials registry number (03167307) will be used as a seed number, if needed.

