Missing data By design, several baseline model covariates cannot be missing, as they are required for minimization during randomization. We distinguish between study dropouts and intervention dropouts. Study dropouts are participants whom withdraw consent, are monotone not available for follow-up visits, or are removed from the trial according to the protocol due to non-compliance (< 60% pills taken). Intervention dropouts are participants whom newly initiate an off-trial antidepressant or are newly prescribed an increased dose of an off-trial antidepressant prescribed before baseline.

Methods to handle missing data are outlined per analysis type below. Where multiple is used, 50 imputed datasets will be computed. Results across datasets will be combined using Rubin's rule.

Modeling In case of covariate imbalance on baseline covariates other than antidepressant use, omega-3 index, age, gender, and hsCRP, these covariates will also be included in the models described below. In case of computational convergence issues, simpler models will be estimated.

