where time t is considered a factor (while also investigating possibility of linearizing time effect) and randomized treatment group (intervention) and the interaction between randomized treatment group and time are included as fixed effects. The baseline values of the minimization factors age, gender, and hsCRP, as well as baseline antidepressant use and omega-3 index are included as covariates. The baseline outcome measure is modeled in the response, not as a covariate. The terms b_{i0} , b_{i1} , and b_{s0} represent participant-specific random intercepts and slopes and site-specific random intercepts. The random effects are assumed to be normally distributed and an unstructured covariance matrix will be assumed. The error term $\varepsilon_i(t)$ is assumed to be normally distributed with mean zero and variance σ^2 , independent of the random effects and is independent over time. An overall treatment effect for CDRS-R score at 36 weeks ($\beta_1 + \beta_{11}$) will be reported with a 95% confidence interval and corresponding p -value.

The competing survival models for time to event r (intervention dropout or study dropout) take the form:

$$\lambda_{ir}(t) = \lambda_{0r} \exp\{\gamma_1 \text{intervention} + \alpha_r m_i(t)\}$$

where the cause-specific Cox models include intervention as a time-independent effect and the estimated true trajectory of CDRS-R as a time-varying effect. The parameters α_r measure the strength of association between the longitudinal outcome and risk of the corresponding dropout event.

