7.2 Secondary endpoints

7.2.1 Confirmatory secondary endpoints

The binary confirmatory secondary outcomes include:

- **Remission**, defined as a CDRS-R total score < 28 at any time up until 36 weeks
- **Response**, defined as a 30% drop in CDRS-R total score at any time up until **12 weeks**
- **Intervention dropout**, defined as initiation of non-randomized antidepressant use while on trial for participants not on a non-randomized antidepressant at baseline or an increase in antidepressant dose while on trial for participants on a non-randomized antidepressant at baseline

Unadjusted proportions per treatment arm will be presented with 95% confidence intervals. To adjust for baseline antidepressant use, omega-3 index, and CDRS score, as well as the minimization factors age, gender, and hsCRP, these binary outcomes will each be assessed using log-binomial models with treatment arm as the effect of interest. Each model will be interpreted in terms of the adjusted risk ratio (RR) comparing the outcome probability in the omega-3 group to that in the placebo group ($RR_{\text{omega-3/placebo}}$). The null hypothesis that the risk ratio is equal to 1 (no difference in risk across treatment groups) will be rejected if the 95% confidence interval for the risk ratio does not include 1. If the 95% confidence interval for the risk ratio is above 1, omega-3 treatment will be considered superior.

These models will include data from all randomized participants and analyze the participant data according to the treatment arms participants were randomized to (as-randomized). Data after intervention dropout will be considered missing. Multiple imputation under MAR will be used to impute longitudinal CDRS-R scores for study and intervention dropouts before the binary outcomes are determined. MI will be performed separately within each treatment arm (White et al 2011) using imputation models containing the minimization factors, baseline antidepressant use and omega-3 index.

As for the primary outcome, a delta-based sensitivity analysis approach will be used to address MNAR. For analysis of intervention dropout, imputation is only needed for participants with study dropout before intervention dropout and no sensitivity analysis is planned.

The continuous confirmatory secondary outcomes include:

- self-reported **quality of life** measured by the KIDscreen-CAT-27 overall score at 36 weeks
- **Depression severity** measured by DIKJ at 36 weeks

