These continuous outcomes will each be assessed using ANCOVA linear regression models with the 36-week measurement as the outcome, treatment arm as the effect of interest, and the baseline measurement, antidepressant use, omega-3 index, CDRS-R score, and the minimization factors age, gender, and hsCRP as covariates.

The treatment coefficient denotes the mean difference in outcome score across the treatment groups. The null hypothesis that the mean scores are equal across treatment groups will be rejected

if the 95% confidence interval for the treatment group coefficient does not include 0. If the 95% confidence interval for the treatment group coefficient is above 0 for KIDscreen-CAT-27 (below 0 for DIKJ), omega-3 treatment will be considered superior with respect to its effect on quality of life (depressive symptoms).

These models will include data from all randomized participants and analyze the participant data according to the treatment arms participants were randomized to (as-randomized). Data after intervention dropout will be considered missing. Multiple imputation under MAR will be used to impute scores at 36 weeks for study and intervention dropouts. MI will be performed separately within each treatment arm (White et al 2011) using imputation models containing the minimization factors, baseline antidepressant use, omega-3 index, and baseline score. As for the primary outcome, a delta-based sensitivity analysis approach will be used to address MNAR.

Sub-domains will be described with tables or figures.

The final confirmatory secondary outcome is:

- the time on trial before initiation of new or increased antidepressant use (intervention dropout).

A Kaplan Meier approach will be used to estimate unadjusted median time to this event overall and per treatment arm. A log rank test will be used to compare time to intervention dropout across treatment arms.

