7.2.2 Supportive secondary endpoints

Effect endpoints

- **Number of days in the hospital**
- **Outpatient service use**

These endpoints will be described using summary statistics across treatment arm.

Safety endpoints

- **Suicidal ideation** from baseline to week 36 will be modeled jointly by a linear mixed effects model for SIQ-Jr score over time combined with Cox regression for time to intervention and study dropout, analogously to the CDRS-R total score primary outcome model.
- **Serious adverse events** from baseline to week 36 will be tabulated per type and treatment arm using the safety analysis set. If appropriate, the difference in proportion (with 95% confidence interval) will be estimated.

8 Changes to the statistical analyses planned in the protocol

Version	Explanation
IICT submission	First version of study plan
Frontiers protocol	Study protocol after funding review and peer review, addition of concomitant treatment description, addition minimization factor for unit type (in-/outpatient), description of sensitivity analyses to account for antidepressant use
UZH protocol	Refinement of secondary (supportive/exploratory) outcomes and their analyses
Statistical analysis plan	Focusing the analysis plan on measures of efficacy and safety for reporting of primary trial results. Updating method for dealing with informative missingness.

9 References

N. M. Laird and J. H. Ware. Random-effects models for longitudinal data. *Biometrics* 1982; 38:963–74

R J A Little and L Yau. Intent-to-treat analysis for longitudinal studies with drop-outs. *Biometrics* 1999; 52:1324–33.

S Mazumdar and K S Liu and P R Houck and C F Reynolds. Intent-to-treat analysis for longitudinal clinical trials: coping with the challenge of missing values. *Journal of Psychiatric Research* 1999; 33:87–95

Michele L Shaffer and Vernon M Chinchilli. Including multiple imputation in a sensitivity analysis for clinical trials with treatment failures. *Contemporary Clinical Trials* 2007 28:130–137

Ian R. White and C Bamias and P Hardy and S. Pocock and J Warner. Randomized clinical trials with added rescue medication: some approaches to their analysis and interpretation. *Statistics in Medicine* 2001; 20:2995–3008.

R version and packages used to generate this report:

R version: R version 4.0.1 (2020-06-06)

Base packages: stats, graphics, grDevices, utils, datasets, methods, base

Other packages: pwr, readxl, reporttools, xtable, knitr

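### The primary joint model adjusts for a baseline omega-3 index that may be missing for some participants, and the SAP has no rule for a missing value

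*Protocol*

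**What the plan says.** **Where the index is used.** SAP 7.1 lists the covariates of the primary joint model: the minimisation factors age, gender and hsCRP, "as well as baseline antidepressant use and omega-3 index are included as covariates". The mixed-model sensitivity analyses in 7.1.2 reuse the longitudinal part of that model. The SIQ-Jr safety model in 7.2.2 is to be built "analogously to the CDRS-R total score primary outcome model". In 7.2.1 the log-binomial models have the same adjustment ("To adjust for baseline antidepressant use, omega-3 index, and CDRS score, as well as the minimization factors age, gender, and hsCRP"), as do the ANCOVA models ("antidepressant use, omega-3 index, CDRS-R score, and the minimization factors age, gender, and hsCRP as covariates"). The index is also named as a variable in the imputation models, and 7.1.1 tests its interaction with treatment and time.

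**Where the index comes from.** Protocol 11.4.3: "We will calculate an omega-3 index based on red blood cell Omega-3 fatty acids content". The flow chart in Protocol 9.1 lists the red-cell sample on a different row from the clinical bloods and hsCRP. Protocol 9.2.2.4 makes the laboratory draw compulsory because minimisation needs it, then adds: "The further bloods shall be taken if possible, but are not mandatory for participation in the clinical trial". Protocol 9.3.1 allows biological sampling up to baseline but not later.

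**What is said about completeness.** SAP 7 (Missing data): "By design, several baseline model covariates cannot be missing, as they are required for minimization during randomization". SAP 7 (Analysis sets): "The full analysis set (FAS) includes all randomized subjects", with exclusions only in exceptional cases. The primary estimand (SAP 4.1) covers all randomised subjects. Protocol 11.5 says that the random coefficient models already take care of missing data, and promises multiple imputation for the other analyses.

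**The concern.** The primary model contains a covariate that some participants may lack and that cannot be obtained afterwards. Neither document says what happens to those participants.

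Likelihood-based mixed and joint models use whatever outcome visits a participant has. They cannot use a participant at all if a fixed baseline covariate is missing, unless that covariate is imputed or modelled. The assurance in Protocol 11.5 was written for the model in Protocol 11.4.2, which has treatment, time and their interaction as its only fixed effects. The SAP added the index and did not revisit the point. Protocol 9.2.2.4 does foresee refusals of extra blood, but treats them as a problem for secondary and tertiary outcomes only.

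At stake is whether the primary result describes everyone randomised or only those who gave an optional sample. Sensitivity analysis 1, meant as the conventional analysis of all participants as randomised, has the same covariate and so would not reveal the problem. If the gap is first noticed at analysis, the choice between dropping the covariate, filling it or deleting participants becomes post hoc.

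**Working it through.** **Step 1. Can the index be missing?** The minimisation factors (SAP 1) are site, age, gender, hsCRP and, at sites offering both, in-/outpatient type. The index is not among them, so the completeness statement in SAP 7 does not reach it. Its sample appears to fall under the non-compulsory bloods and cannot be collected after baseline.

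**Step 2. Does any planned method fill it?**

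| Analysis | Uses index | Planned handling of a missing index |
|---|---|---|
| CDRS-R joint model (7.1) | yes | none; the dropout submodels address missing outcomes |
| Mixed-model sensitivity analyses 1 to 3 (7.1.2) | yes | none |
| SIQ-Jr joint model (7.2.2) | yes, by analogy | none |
| Delta-based imputation (7.1.2) | yes | index named as a predictor; its own imputation not stated |
| Log-binomial and ANCOVA models (7.2.1) | yes | imputation described for scores; index named as a predictor |
| Unadjusted proportions, Kaplan-Meier, log-rank (7.2.1) | no | not affected |

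**Step 3. Reproduce the planned sample size.** Inputs from SAP 6.1: SMD 0.4, power 80%, two-sided alpha 0.05, 1:1 allocation. The two-sample t-test needs 99.08 per arm. SAP 6.2 states 10% loss to follow-up: 99.08 / 0.90 = 110.09, rounded up to 111 per arm, 222 in total. This matches the SAP. Without that loss, 111 per arm gives 84.3% power, so the 80% corresponds to 111 × 0.90 = 99.9 evaluable per arm.

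**Step 4. Illustrate the loss.** The documents do not give the share without an index, m, so 5% to 20% is an assumption. With n = 99.9 × (1 − m) per arm, the noncentrality is 0.4 × √(n/2), and power is the probability that a noncentral t on 2n − 2 degrees of freedom exceeds the two-sided 5% critical value.

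| m | left out of 220 | n per arm (99.9 base) | power | n per arm (111 base, no other loss) | power |
|---|---|---|---|---|---|
| 0% | 0 | 99.9 | 80.3% | 111.0 | 84.3% |
| 5% | 11 | 94.9 | 78.3% | 105.4 | 82.4% |
| 10% | 22 | 89.9 | 76.0% | 99.9 | 80.3% |
| 20% | 44 | 79.9 | 71.0% | 88.8 | 75.5% |

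This is an unadjusted comparison at one time point. It is not the joint model, and it ignores any precision gained from adjustment.

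**The case against.** The strongest reply is that this is only an unstated detail of possibly negligible size. Several parts of that reply stand.

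- **Analysis set.** A reader might infer that participants without an index leave the full analysis set. They do not: the set is defined by randomisation, and no text says they are deleted. What they drop out of is the fitted model.
- **Completeness statement.** A reader might infer that the SAP wrongly claims all its covariates are complete. It says this only of several covariates, and that is correct. It is silent on the index.
- **Secondary analyses.** A reader might infer that every adjusted analysis is affected. Protocol 11.5 promises multiple imputation outside the random coefficient models, and the SAP names the index in the imputation models. Imputing it with the scores is a natural reading, though not stated. The firm gap is the two joint models and the mixed-model sensitivity analyses.
- **Optional sample.** Protocol 9.2.2.4 also says that blood left from the routine tests is stored for fatty acids, and its list of draws names no separate red-cell tube. Some index values may therefore come from the compulsory draw. The separate row in the flow chart and the optional status of further blood point the other way, so the sample appears optional but this is not certain.
- **Size.** No missing share is given. Research bloods are drawn together to limit burden, so the share may be small. On the 111 base, power is still about 80% with 10% missing.

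None of this supplies a rule for the primary model. The one general assurance, that such models already handle missing data, is not true of a missing covariate.

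**Conclusion.** The gap is real and falls on the primary analysis. As written, the CDRS-R joint model, the SIQ-Jr joint model and the mixed-model sensitivity analyses would be fitted without any randomised participant who lacks a baseline index, contrary to the all-randomised estimand. For the log-binomial, ANCOVA and delta analyses the SAP needs only to make explicit what its imputation plan arguably implies.

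The size is unknown. With about 100 evaluable per arm, the cost is roughly 2 percentage points of power at 5% missing, 4 at 10% and 9 at 20%, under the assumptions above. A reader might infer a biased treatment comparison. The documents do not support that: the sample is due before baseline, so its absence should not depend on arm. The harm is lost precision and a population restricted to those with a sample.

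**What to change.** Add to SAP 7 (Missing data), before unblinding:

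1. Where the index is only an adjustment covariate, a missing baseline value is replaced by the overall mean, or by a regression prediction from baseline variables that does not use arm, and a missing indicator is added. Every randomised participant then stays in the fitted model.
2. The multiple imputation models for the secondary and delta analyses impute the index as well as the scores.
3. The number of missing index values is reported by arm.
4. The interaction analysis in 7.1.1 is exempt from mean-filling, which would distort the effect being tested. Run it on participants with a measured index, fitting both compared models to that same set, or use multiply imputed values.

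The cost is a few lines of SAP text, slightly more analysis work and a small loss of adjustment efficiency for the filled values. No new data are needed.
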